7. RESEARCH METHODS

7.1. Study Design

Observational, descriptive study of a retrospective cohort of adult patients diagnosed with NVAF in selected Health Maintenance Organization (HMO) of Colombia. These patients will be identified from the drug claim database, whose index date of the study will be the first prescription with any of the oral anticoagulants, that is, they are patients with NVAF for the first time starting a therapy with any of the NOACs between January 1, 2013 and June 30, 2018 and follow up period will be among January 2013 to July 2019, to ensure that the last patients can provide follow-up for one year. Patients will be required to have an NVAF diagnosis before or on the index date and health plan for 6 months pre-index date (baseline period).

Following, it will be verified that the patients meet the inclusion and exclusion criteria of the study. Once patients are selected and with the index date of each patient, they will be followed-up until discontinuation, switch of treatment, death or first event of stroke/ systemic embolism, major bleeding event, death or end of follow-up. Patients who are lost to follow-up, change of HMO and do not have access to the medical record will be considered as missing (Figure 1).

Figure 1. Study Design

[figure not shown]
The information will be analyzed in two moments: (i) the period of the index date, where the baseline information of patients will be collected; (ii) and the follow-up period, during this period the clinical results will be evaluated as well as the continuation of the treatment in the study population and for specific subpopulations.

Those patients who initiated treatment with any oral anticoagulant between January 2013 and June 30, 2018 will be included. This means that patients who start warfarin and NOACs would

be included within this period. Patients who initiate NOACs within the established period and who have been exposed to warfarin before 2013 will also be included.

Only the exposure period will be considered with the initial treatment, even in those patients who were on warfarin treatment before 2013, in the latter, the follow-up will be the treatment initiation with a NOAC in case of change after 2013. Follow-up will be carried out until the patient has a switch of treatment, discontinuation, death, first stroke/ systemic embolism, or major bleeding, or until end of follow-up, June 30, 2019 (Figure 2).

Figure 2. Inclusion of Patients

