7.2. Setting

The study will be conducted with the Audifarma patient cohort that meets the inclusion and exclusion criteria between the periods from January 2013 to June 30, 2018. The follow up period will be among January 2013 to July 2019, to ensure that the last patients can provide follow-up for one year.

This study will include the entire population in which medical records can be accessed. This will depend on the authorization of the HMOs for review of medical records. Participating patients will be followed-up until the patient has a stroke/systemic embolism, major bleeding, discontinuation, change of treatment or until the data collection period is completed.

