Persistence	Clinical outcome	Claim databases	Yes, No
OAC treatment	Treatment	Claim databases	Warfarin, apixaban, rivaroxaban, dabigatran
Diagnosis at index date	Treatment	Claim databases	Diagnosis AF based on ICD-10
Date of OAC prescription	Treatment	Claim databases	Date reported dd/mm/yy
Dosage of the initial OAC treatment	Treatment	Claim databases	Mg per dose
Initial frequency of OAC treatment	Treatment	Claim databases	Number of doses at initial OAC treatment
OAC escalation	Treatment	Claim databases	Yes, No
Type of OAC escalation	Treatment	Claim databases	Dose increase or dose decrease
Time to OAC escalation	Treatment	Claim databases	Date reported dd/mm/yy
CCI			

Variable	Role	Data source (s)	Operational definition
CCI			
INR testing monthly in patients with warfarin	Treatment	Medical record	INR reported in the medical record per month
Switch to another OAC treatment:	Treatment	Claim databases	Yes, No
Time to Switch to another OAC treatment	Treatment	Claim databases	Date reported dd/mm/yy
Causa de cambio	Treatment	Medical record	Adverse events, effectiveness, adherence, patient preference, administrative problems, not reported, others
Concomitant therapies by OAC prescription	Treatment	Medical record	NSAIDs, Angiotensin-converting-enzyme (ACE) inhibitors, Amiodarone, Beta-blockers, Angiotensin II receptor blockers (ARBs), Aspirin, Clopidogrel, Digoxin, Diuretics, calcium blockers, statins, proton pump inhibitor, selective H2 antagonists, antidiabetics, insulin, serotonin reuptake inhibitors
Previously exposed to warfarin	Treatment	Claim databases	Yes, No

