7.3.1. Definition of outcome variables

- **OAC escalation:** The dose escalation of the OAC dose will be considered as a dose frequency according to the index dose, as well as the follow-up doses. The proportion of patients experiencing "dose increase", "dose decrease" or "no change" during follow-up with respect to the index dose will be measured, and the time to dose increase or decrease will be calculated.

C
C
I

C
C
I

- **Switch of treatment:** A switch among anticoagulants will be defined as a prescription filled for non-index anticoagulants within +/- 30 days after the date of discontinuation.
- **Persistence:** Persistence will be defined as the time under OAC therapy, calculated as the time in days from the index date to the date of discontinuation or change to treatment. As previously stated, discontinuation will be defined as a change of treatment, that is, to another OAC, or when there is no evidence of a prescription for 60 days from the last supply delivered, whichever comes first.

Therefore, if a patient does not receive his next prescription for the OAC therapy within 60 days after the end of the previous prescription, it will be considered that he discontinued therapy, and the date of the last prescription will be considered as the final date of persistence.

Persistence with OAC therapy will be considered during the period of individual patient follow-up. Patients will be censored at the end of their follow-up period.

- **Major bleeding:** Patients presenting any of the following diagnoses during the follow-up period:

ICD-10	Description
I60	Subarachnoid haemorrhage
I61	Intracerebral haemorrhage
I62	Other nontraumatic intracranial haemorrhage
I690	Sequelae of subarachnoid haemorrhage
I691	Sequelae of intracerebral haemorrhage
I692	Sequelae of other nontraumatic intracranial haemorrhage
S064	Epidural haemorrhage
S065	Traumatic subdural haemorrhage
S066	Traumatic subarachnoid haemorrhage
I850	Oesophageal varices with bleeding
K250	Acute with haemorrhage

Apixaban

B0661148- NON-INTERVENTIONAL STUDY PROTOCOL

Final, 10 October 2019

ICD-10	Description
K252	Acute with both haemorrhage and perforation
K254	Chronic or unspecified with haemorrhage
K256	Chronic or unspecified with both haemorrhage and perforation
K260	Acute with haemorrhage
K262	Acute with both haemorrhage and perforation
K264	Chronic or unspecified with haemorrhage
K266	Chronic or unspecified with both haemorrhage and perforation
K270	Acute with haemorrhage

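### Persistence, part of a primary objective, is coded Yes/No with no time point in Table 1 but defined as censored days in 7.3.1, and the only legible time-to-discontinuation analysis is exploratory and limited to event-free patients

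*Combined protocol and SAP*

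**What the plan says.** Section 6 lists persistence among the treatment patterns to be described under the primary objectives. The plan then gives it two forms.

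- **Table 1 (section 7.3):** "Persistence Clinical outcome Claim databases Yes, No". No time point is attached.
- **Section 7.3.1:** "Persistence will be defined as the time under OAC therapy, calculated as the time in days from the index date" to discontinuation or change of treatment. Discontinuation means a change to another anticoagulant, or 60 days without a new supply. The section continues "Persistence with OAC therapy will be considered during the period of individual patient follow-up", and then "Patients will be censored at the end of their follow-up period".

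On timing, section 7.1 describes patients "starting a therapy with any of the NOACs between January 1, 2013 and June 30, 2018", with observation "or until end of follow-up, June 30, 2019". Section 7.2 gives the purpose of the last year: "to ensure that the last patients can provide follow-up for one year". Follow-up can end sooner: "Follow-up will be carried out until the patient has a switch of treatment, discontinuation, death, first stroke/ systemic embolism, or major bleeding".

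On analysis, section 7.7 summarises categorical variables by counts and percentages. It plans Kaplan-Meier curves for clinical outcomes, under an exploratory heading. Under the same heading it plans a similar analysis of time to change of treatment (the sentence is partly blacked out). The abstract's statistical paragraph has the sentence in full and names discontinuation as well. Both versions confine this analysis to patients without stroke/systemic embolism or major bleeding. No section names a time at which a percentage persistent will be reported.

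**The concern.** A Yes/No status judged over each patient's own follow-up asks a different question of each patient. Someone indexed in January 2013 must stay on treatment for six and a half years to count as Yes; someone indexed in June 2018 needs one year. On the plain reading, a patient whose follow-up ends early at a stroke while still on treatment also counts as Yes. A percentage built this way refers to no time on treatment, and it shifts with the calendar mix of starters even when behaviour is identical.

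The days definition with censoring would avoid this, but the only legible analysis that uses it has two weaknesses. It is labelled exploratory although persistence belongs to a primary objective. It also drops patients according to something that happens after index. Because follow-up stops at discontinuation, patients who stay on treatment longer have more time in which to have an event and be removed. If events and stopping were independent, the restricted curve would understate persistence. If patients heading for an event also tend to stop sooner, the direction could reverse. The documents give no event or stopping rates from which to size this.

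**Working it through.** **Inputs from the documents.** First index date January 1, 2013; last index date June 30, 2018; end of follow-up June 30, 2019 (section 7.1); study size 7,500 (section 7.5).

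**The plan's own figure.** June 30, 2018 to June 30, 2019 is 365 days, and 365/365.25 = 1.00 year. This reproduces the stated one year for the last patients.

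**Range of potential follow-up.** January 1, 2013 to June 30, 2019 is 2,371 days, and 2,371/365.25 = 6.49 years. Some sentences give July 2019 as the end; with July 31, 2019 the range is 1.08 to 6.58 years. These are administrative limits, and actual follow-up can be shorter.

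**Assumptions for the illustration.** The documents give no discontinuation rate and no distribution of start dates. I assume the same constant hazard h for everyone, start dates uniform over the window and no competing events. True 12-month persistence S is varied over 40%, 60% and 80%, with h = −ln(S).

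**Formulas.** A patient with follow-up f is still on treatment at its end with probability exp(−h·f). With f uniform on (a, b), the crude percentage of Yes is

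[exp(−h·a) − exp(−h·b)] / [h·(b − a)].

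For S = 60%: h = 0.511, a = 0.999, b = 6.491, giving (0.600 − 0.036)/(0.511 × 5.492) = 0.201.

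The earlier and later halves of starters are split at the midpoint of follow-up, (0.999 + 6.491)/2 = 3.745 years.

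| True 12-month persistence | Earliest starter | Latest starter | Earlier half | Later half | All patients, crude Yes |
|---|---|---|---|---|---|
| 40% | 0.3% | 40% | 1.2% | 14.6% | 7.9% |
| 60% | 3.6% | 60% | 7.9% | 32.3% | 20.1% |
| 80% | 23.5% | 80% | 32.4% | 59.8% | 46.1% |

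Down the last column, the crude figure does respond to true persistence. Across each row, it also responds to start date with behaviour held fixed.

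**Kaplan-Meier on the same set-up.** With 7,500 simulated patients per group, the estimate just before 12 months (0.99 years) was:

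| True 12-month persistence | All | Earlier half | Later half |
|---|---|---|---|
| 40% | 40.3% | 39.6% | 41.3% |
| 60% | 60.3% | 60.0% | 60.0% |
| 80% | 80.5% | 80.5% | 80.7% |

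With independent censoring, the curve recovers the true value whatever the start date.

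**Limit at 12 months.** The last starter has 365 days of follow-up. A stop is recognised only after 60 days without supply, so a supply that runs out after day 365 − 60 = 305 cannot be confirmed as discontinued by June 30, 2019.

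**The case against.** The best defence is that 7.3.1 already contains a proper time-to-event definition, in days and with explicit censoring, and that a Kaplan-Meier-type analysis of time to discontinuation is planned. Elsewhere Table 1 pairs a Yes/No row with a time row (stroke, bleeding, dose escalation, switch), so the persistence Yes/No may be meant only as an event indicator. Rows near it are blacked out, as is text just before the definition of discontinuation. Nobody can therefore say that a time-to-discontinuation variable is missing. No sentence says that a crude percentage will be the persistence result; that follows only from applying the general rule for categorical variables to this row. All of this stands.

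It does not settle the matter. The two forms remain unreconciled, no reporting time is set, and the legible curve is exploratory and restricted to event-free patients.

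A reader might go further and infer that later-adopted drugs will look spuriously more persistent. With an assumed hazard of 0.30 per year, starts spread over 2013 to mid-2018 give 36.3% Yes, and starts spread over 2016 to mid-2018 give 52.1%, a gap of about 16 points. The documents do not support this as a finding. They give neither that hazard nor any uptake pattern by drug, and 7.7 rules out a treatment comparison. Percentages set out for the four cohorts of section 7.2.3 could still be read side by side, but that is not a planned inference.

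**Conclusion.** The point holds in a limited form. Table 1 and 7.3.1 describe persistence differently, no time point is fixed, and the one legible time-to-discontinuation analysis is exploratory and conditions on post-index events, although persistence is part of a primary objective. If a crude percentage of Yes were reported, it would mix start date with time on treatment. Under the stated assumptions, 40%, 60% or 80% true 12-month persistence would appear as about 8%, 20% or 46%. Those figures rest on a constant hazard, uniform start dates and no competing events. They illustrate the problem and do not predict this study's results.

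Two stronger statements should not be made. One is that the percentage reflects start date instead of time on treatment: it reflects both, as the move from 8% to 46% shows. The other is that the plan treats persistence as Yes/No alone: the days definition and the censoring sentence are in 7.3.1.

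**What to change.** - **Section 7.7:** make the persistence result a Kaplan-Meier estimate of time to discontinuation or switch in all patients, overall and by cohort, as the analysis for the primary objective. Censor at stroke/systemic embolism, major bleeding, death, loss to follow-up or June 30, 2019.
- **Reporting:** give the estimate at 12, 24 and 36 months from index, with 95% confidence intervals and numbers at risk. State that it assumes independent censoring.
- **Section 7.7 and the abstract:** remove the restriction to patients without stroke/systemic embolism or major bleeding from the time-to-discontinuation analysis.
- **Table 1:** keep the Yes/No only as the event indicator for this curve, refer it to the 7.3.1 definition, and do not report it as a crude percentage.

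The cost is one table row, short edits to 7.7 and the abstract, and a little more analysis work. Dispensing dates are already in the claims database. One limitation remains: every patient can reach 12 months administratively, but under the 60-day rule the status of the latest starters may be unconfirmed at that point, and the report should say so.

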Leukemia	Clinical characteristic	Medical record	Yes, No

PFIZER CONFIDENTIAL

Variable	Role	Data source (s)	Operational definition
Malignant lymphoma	Clinical characteristic	Medical record	Yes, No
Peptic ulcer disease	Clinical characteristic	Medical record	Yes, No
Metastatic solid tumor	Clinical characteristic	Medical record	Yes, No
History of ischemic or hemorrhagic stroke	Clinical characteristic	Medical record	Yes, No
History of TIA	Clinical characteristic	Medical record	Yes, No
History of de tromboembolismo	Clinical characteristic	Medical record	Yes, No
Enfermedad coronaria	Clinical characteristic	Medical record	Yes, No
History of de hemorragia gastrointestinal	Clinical characteristic	Medical record	Yes, No
History of Intracranial bleeding	Clinical characteristic	Medical record	Yes, No
History of Other bleeding	Clinical characteristic	Medical record	Yes, No
Bleeding history or predisposition at start OAC treatment	Clinical characteristic	Medical record	Yes, No
INR > 60% at start OAC treatment	Clinical characteristic	Medical record	Yes, No
Use of aspirin at start OAC treatment	Clinical characteristic	Medical record	Yes, No
Use of clopidogrel at start OAC treatment	Clinical characteristic	Medical record	Yes, No
Use of NSAIDs at start OAC treatment	Clinical characteristic	Medical record	Yes, No
HASBLED at start OAC treatment	Clinical characteristic	Medical record	Score – number higher than 0
CHA2DS2-VASc at start OAC treatment	Clinical characteristic	Medical record	Score – number higher than 0
Anaemia at start OAC treatment	Clinical characteristic	Medical record	Yes, No
Stroke	Clinical outcome	Medical record	Yes, No
Time to stroke	Clinical outcome	Medical record	Date of event dd/mm/yy

Pfizer Confidential

Variable	Role	Data source (s)	Operational definition
Type of stroke	Clinical outcome	Medical record	Ischemic stroke, Haemorrhagic or not specified
Pulmonary embolism	Clinical outcome	Medical record	Yes, No
Time to pulmonary embolism	Clinical outcome	Medical record	Date of event dd/mm/yy
Gastrointestinal bleeding	Clinical outcome	Medical record	Yes, No
Time to gastrointestinal bleeding	Clinical outcome	Medical record	Date of event dd/mm/yy
Intracranial bleeding	Clinical outcome	Medical record	Yes, No
Time to Intracranial bleeding	Clinical outcome	Medical record	Date of event dd/mm/yy
Other major bleeding	Clinical outcome	Medical record	Yes, No
Time to other major bleeding	Clinical outcome	Medical record	Date of event dd/mm/yy
CCI			

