K272	Acute with both haemorrhage and perforation
K274	Chronic or unspecified with haemorrhage
K276	Chronic or unspecified with both haemorrhage and perforation
K280	Acute with haemorrhage
K282	Acute with both haemorrhage and perforation
K284	Chronic or unspecified with haemorrhage
K286	Chronic or unspecified with both haemorrhage and perforation
K290	Acute haemorrhagic gastritis
K625	Haemorrhage of anus and rectum
K920	Haematemesis
K921	Melaena
K922	Gastro-intestinal haemorrhage, unspecified
D62	Acute posthaemorrhagic anaemia
H356	Retinal haemorrhage
H431	Vitreous haemorrhage
H450	Vitreous haemorrhage in diseases classified elsewhere
H922	Otorrhagia
I312	Haemopericardium, not elsewhere classified
J942	Haemothorax
R04	Haemorrhage from respiratory passages
K661	Haemoperitoneum
M250	Haemarthrosis
N02	Recurrent and persistent haematuria
N938	Other specified abnormal uterine and vaginal bleeding
N939	Abnormal uterine and vaginal bleeding, unspecified
N950	Postmenopausal bleeding
R31	Unspecified haematuria
R58	Haemorrhage, not elsewhere classified
T792	Traumatic secondary and recurrent haemorrhage

- Ischemic stroke:** Patients who report the following diagnoses in the medical history during the follow-up period:

ICD-10	Description
I63	Cerebral infarction
I64	Stroke, not specified as haemorrhage or infarction

Except I63.6 Cerebral infarction due to thrombosis of cerebral veins, non-pyogenic

- Hemorrhagic stroke:** Patients presenting the following diagnosis in the medical record:

PFIZER CONFIDENTIAL

ICD-10	Description
I60	Subarachnoid haemorrhage
I61	Intracerebral haemorrhage
I62	Other nontraumatic intracranial haemorrhage

- **Systemic embolism:** Patients who report any of the following diagnoses:

ICD-10	Description
I74	Arterial embolism and thrombosis

Definition of covariates

- **Age:** Categorical variable, continues in years. It will be defined from the index date and will be used to assign patients to the following age categories:

18 - 49
 50 - 59
 60 - 69
 70 - 79
 ≥ 80 years old.

- **Charlson Index:** Charlson comorbidity index will be created during the reference period taking into account the following score:

1 point each:

- *Myocardial infarction*

ICD-10	Description
I21	Acute myocardial infarction
I22	Subsequent myocardial infarction
I252	Old myocardial infarction

- *Congestive heart failure*

ICD-10	Description
I110	Hypertensive heart disease with (congestive) heart failure

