Bleeding (gastrointestinal, intracranial, other)	I60 Subarachnoid haemorrhage I61 Intracerebral haemorrhage I62 Other nontraumatic intracranial haemorrhage S064 Epidural haemorrhage S065 Traumatic subdural haemorrhage S066 Traumatic subarachnoid haemorrhage I850 Oesophageal varices with bleeding K250 Acute with haemorrhage K252 Acute with both haemorrhage and perforation K254 Chronic or unspecified with haemorrhage K256 Chronic or unspecified with both haemorrhage and perforation K260 Acute with haemorrhage K262 Acute with both haemorrhage and perforation K264 Chronic or unspecified with haemorrhage K266 Chronic or unspecified with both haemorrhage and perforation K270 Acute with haemorrhage K272 Acute with both haemorrhage and perforation K274 Chronic or unspecified with haemorrhage K276 Chronic or unspecified with both haemorrhage and perforation K280 Acute with haemorrhage K282 Acute with both haemorrhage and perforation K284 Chronic or unspecified with haemorrhage K286 Chronic or unspecified with both haemorrhage and perforation K290 Acute haemorrhagic gastritis K625 Haemorrhage of anus and rectum K920 Haematemesis K921 Melaena K922 Gastro-intestinal haemorrhage, unspecified D62 Acute posthaemorrhagic anaemia H356 Retinal haemorrhage H431 Vitreous haemorrhage H450 Vitreous haemorrhage in diseases classified elsewhere H922 Otorrhagia

PFIZER CONFIDENTIAL

Variable	Operacional definition ICD-10
	I312 Haemopericardium, not elsewhere classified J942 Haemothorax R04 Haemorrhage from respiratory passages K661 Haemoperitoneum M250 Haemarthrosis N02 Recurrent and persistent haematuria N938 Other specified abnormal uterine and vaginal bleeding N939 Abnormal uterine and vaginal bleeding, unspecified N950 Postmenopausal bleeding R31 Unspecified haematuria R58 Haemorrhage, not elsewhere classified T792 Traumatic secondary and recurrent haemorrhage
Systemic embolism	I74 Arterial embolism and thrombosis
Alcohol consumption	E244 Alcohol-induced pseudo-Cushing's syndrome E52 Niacin deficiency [pellagra] G312 Degeneration of nervous system due to alcohol G621 Alcoholic polyneuropathy G721 Alcoholic myopathy I426 Alcoholic cardiomyopathy K292 Alcoholic gastritis K70 Alcoholic liver disease K860 Alcohol-induced chronic pancreatitis O354 Maternal care for (suspected) damage to foetus from alcohol T51 Toxic effect of alcohol Z714 Alcohol abuse counselling and surveillance Z721 Alcohol use

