7.9 Limitations of the research methods

This study, as other observational studies, has some limitations; these are the result of the type of study and the source of information used. It is possible that there is some misclassification of the diagnoses of patients with NVAF as in turn in the diagnoses of the outcomes. For example, in the medical record, it is possible for the Investigator to use indirect information or to relate some type of approximation to obtain the variable or information of interest or to perform. Although this is a risk, the presence has been mitigated through a clear definition of the outcomes and with the case report format, which allows the Investigator to extract the relevant information only.

As for the claim database, a limitation is that prescription does not indicate whether the patient actually took the therapy as prescribed in both dosage and frequency.

On the other hand, this study will not obtain information related to hospitalizations of patients during the follow-up period; therefore, in the event of having any during this period it will not be known if the patient continued therapy. It is worth noting that these types of limitations are not differential among the cohorts of therapies to assess.

In spite of the limitations previously described, this information is very valuable, especially because it allows linking the claim information of medications with the medical records of each patient, providing a large sample size with a significant number of variables.

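### Major bleeding in Section 7.3.1 carries no severity criterion: it is the plan's unlabelled baseline bleeding list plus three sequelae codes, so it measures recorded bleeding and is likely to overstate major bleeding

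*Combined protocol and SAP*

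**What the plan says.** Section 7.3.1 (Definition of outcome variables) defines major bleeding as "Patients presenting any of the following diagnoses during the follow-up period" and then gives a code list. No condition on haemoglobin fall, transfusion, critical site, admission or death is attached. The list runs from intracranial haemorrhage to R04 ("Haemorrhage from respiratory passages"), R31 ("Unspecified haematuria") and R58 ("Haemorrhage, not elsewhere classified"). It also includes I69.0 ("Sequelae of subarachnoid haemorrhage"), I69.1 and I69.2.

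Table 2, in the same section, defines a baseline variable headed "Bleeding (gastrointestinal, intracranial, other" by code list, without the word major.

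Table 1 (Section 7.3) takes the bleeding outcomes from the medical record as Yes/No fields with event dates: gastrointestinal, intracranial, and "Other major bleeding". It gives no grading rule for any of them.

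Section 7.7 plans cumulative incidence and Kaplan-Meier curves for major bleeding. It also plans a time-to-switch analysis restricted to patients with neither stroke/systemic embolism nor major bleeding. Section 7.1 ends a patient's follow-up at the first such event. Section 7.9 states that "this study will not obtain information related to hospitalizations of patients during the follow-up period", and cites the clarity of the outcome definitions as protection against misclassification.

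**The concern.** A reader of the report will take a major-bleeding curve to describe severe bleeding. If the definition admits a single nosebleed, haematuria or postmenopausal-bleeding code on the same footing as an intracranial haemorrhage, the curve describes something broader.

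The effect is not confined to the safety result. The same definition ends follow-up and decides who enters the time-to-switch analysis. A non-severe bleed therefore stops observation for stroke/systemic embolism and removes a patient for whom bleeding may have been a reason to change treatment.

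The sequelae codes raise a separate problem: they describe the after-effects of a haemorrhage, which may have happened before the index date.

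**Working it through.** **Inputs.** The major-bleeding list (Section 7.3.1), the Table 2 bleeding row, the HAS-BLED B list (Section 7.3.1), the Table 1 outcome fields, and the follow-up and analysis rules (Sections 7.1 and 7.7). The plan states no bleeding rate, event target or precision, so there is no figure of its own to reproduce.

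**Step 1: compare the two lists code by code.**

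| Group | Major bleeding (7.3.1) | Table 2 bleeding |
|---|---|---|
| I60, I61, I62 | 3 | 3 |
| I69.0, I69.1, I69.2 | 3 | 0 |
| S06.4, S06.5, S06.6 | 3 | 3 |
| I85.0 | 1 | 1 |
| K25-K28, each with .0, .2, .4, .6 | 16 | 16 |
| K29.0, K62.5, K92.0, K92.1, K92.2 | 5 | 5 |
| D62, H35.6, H43.1, H45.0, H92.2, I31.2, J94.2, R04, K66.1, M25.0, N02, N93.8, N93.9, N95.0, R31, R58, T79.2 | 17 | 17 |
| Total | 48 | 45 |

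The outcome list minus Table 2 is {I69.0, I69.1, I69.2}. Table 2 minus the outcome list is empty. Apart from the sequelae codes, the word major selects nothing.

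**Step 2: count the codes that carry no severity information.** R04, R31, N02, N93.8, N93.9, N95.0, H92.2 and R58 make 8 of 48, or 8/48 = 17% of the codes. This is a share of codes, not of events. The documents do not say how often each code occurs.

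**Step 3: trace where the definition is used.**
- It is the event in the major-bleeding incidence and Kaplan-Meier curves (Section 7.7).
- It ends follow-up (Section 7.1), so time at risk for stroke/systemic embolism stops at the code. The persistence definition censors patients at the end of follow-up, so persistence is cut at the same point.
- It excludes patients from the time-to-switch analysis (Section 7.7).

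**Step 4: possible size, by assumption only.** Let q be the share of captured first events that would meet a severity-based definition. Early in follow-up, the ratio of reported to true major-bleeding incidence is about 1/q. The documents give no value for q, so a range is shown:

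| q (assumed) | 1/q |
|---|---|
| 0.9 | 1.11 |
| 0.7 | 1.43 |
| 0.5 | 2.0 |
| 0.3 | 3.3 |

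The ratio is approximate. It ignores severe bleeds that follow a first non-severe one, and severe bleeds whose code is not on the list.

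**The case against.** The strongest counter-argument is that outcomes are not read mechanically from codes. Section 7.6.1 has trained physicians abstract the charts on a form validated against records, with completion instructions still to be written, and the Table 1 field is named "Other major bleeding". An abstractor might not tick it for a trivial nosebleed. This stands in part: it makes overstatement likely rather than certain. It does not cure the definition, because no written criterion tells an abstractor what major means, and the only operational definition given is the code list.

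The weight is also limited. Time to bleeding is an exploratory, descriptive objective, no treatment comparison is planned, and Section 7.9 already admits outcome misclassification. Table 1 records intracranial and gastrointestinal bleeding separately, so those sites can be shown on their own. That is correct, and the fix uses it.

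Some stronger readings are tempting but not supported:
- **That the list captures all coded bleeding.** It does not. I98.3, K22.6 and K76.2 (HAS-BLED B) and D68.3, D69.8, D69.9, H31.3 and I23.0 (HAS-BLED S) are absent from it.
- **That absence from HAS-BLED B marks a code as minor.** B omits 21 of the 48 outcome codes, including S06.4-S06.6 and I31.2, so it does not sort codes by severity.
- **That major bleeding is the study's only safety outcome.** Other safety outcomes are blacked out, so this cannot be known.

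**Conclusion.** The point holds as a defect of definition and labelling. Section 7.3.1 has no severity criterion, and its list equals Table 2's bleeding list plus I69.0-I69.2; this is exact and needs no assumption. Followed as written, the plan reports recorded bleeding from the listed codes as major bleeding, ends follow-up on it, and restricts the time-to-switch analysis by it.

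The direction, overstatement of major bleeding, is likely. It rests on some listed events being non-severe and on abstractors not applying an unwritten threshold. A reader might infer a specific inflated rate; the documents do not support one, and the 1/q range above illustrates scale rather than estimating it. The sequelae codes can add pre-index haemorrhages as new events, by an amount that is likewise unknown.

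**What to change.** 1. Rename the full-list outcome any recorded bleeding and analyse it as time to the first listed code. It must not be formed by adding a major and a non-major incidence: a patient can have both, and first-event incidences do not add.
2. Report intracranial and gastrointestinal bleeding separately, using the existing Table 1 fields.
3. Reserve major bleeding for a pre-specified subset that excludes R04, R31, N02, N93.8, N93.9, N95.0, H92.2 and R58. Assign K62.5, D62 and T79.2 explicitly to a tier. Split the Table 1 field "Other major bleeding" to match, and let only the major subset end follow-up and define the exclusion from the time-to-switch analysis.
4. Remove I69.0-I69.2 as incident events.

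After step 4 the any-recorded-bleeding list has 48 - 3 = 45 codes. The major subset then has 45 - 8 = 37 codes if K62.5, D62 and T79.2 all stay in, and 37 - 3 = 34 if none does, provided no other code is moved.

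**Cost.** A revised code table, one extra abstraction field, and chart follow-up beyond non-major bleeds. There will be fewer major-bleeding events, and the tier of a few codes is a matter of judgement. Code alone remains an imperfect proxy for severity, more so without hospitalisation data, and Section 7.9 should say so.
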